13.3.1 Informed Consent/Assent Process (in Case of a Minor)

• Persons under 18 years of age are not eligible to participate. COVID19 has 0% mortality in children, and rate of progression to symptomatic disease may likely be different. Furthermore, pediatric dosing is weight-based, making remote administration more complicated.

13.4 Exclusion of Women, Minorities, and Children

- Persons under 18 years of age are not eligible to participate. COVID19 has 0% mortality in children and young adults.
- Non-English speaking adults are not eligible as the webpage and consents will only be available in English.

13.5 Subject Confidentiality

- Interaction will be via internet-based RedCAP ECRFs conforming to required U.S. privacy and server security standards.
- Clinical data will be entered into a study-specific database by designated staff on a regular basis from completed electronic Case Record Forms (eCRF). Access to the database will be given to authorized personnel only (members of the immediate study team). eCRF and trial documents will be kept in a secure database.
- Documentation, data and all other information generated will be held in strict confidence. No information concerning the study or the data will be released to any unauthorized third party, without the prior written approval of the participant except as necessary for monitoring by the IRB or public health authorities
- No participant identifying information will be disclosed in any publication or at any conference activities arising from the study.

13.6 Future Use of Stored Specimens

• No specimens are to be collected.

14 DATA HANDLING AND RECORD-KEEPING

14.1 Data Management Responsibilities

Investigators will maintain a REDCAP database of study records.

Survey forms will be self-completed by study participants.

14.2 Data Capture Methods

• Data will be obtained via internet-based REDCAP forms.

14.3 Types of Data

 Participants will be asked to provide data regarding COVID19 exposure timing and location. They will also be asked to provide ongoing symptom reports during the follow-up period.

14.4 Timing/Reports

- An enrollment progress report will be generated monthly
 - Participants Enrolled
 - Participants on study
 - Participants completed the study
 - Lost to Follow Up
 - Cumulative COVID19 (pooled, both arms)
 - Cumulative Hospitalizations (pooled, both arms)
- A data safety monitoring board (DSMB) will review data after every 450 participants complete 90 days of follow-up.
- De-identified data will be shared with the research team members for analysis.

14.5 Study Records Retention

- No paper documents will be retained or stored.
- Digital records will be kept in a secure server setting.

14.6 Protocol Deviations

Protocol violations will be reported to the IRB of record.

15 PUBLICATION POLICY

Publication will be expeditiously made with a full, de-identified data made available.

Appendix A: Sub study

Sub study Title	Pre-exposure Prophylaxis for SARS-Coronavirus-2: A Pragmatic Randomized Clinical Trial: A sub-study of peripheral blood correlatives
Objectives	This is a sub study for correlative sample collection of blood to evaluate:
	 Circulating antibody (IgG or IgM) presence specific for COVID-19 virus protein at baseline
	a. This is determined by ELISA from serum or plasma using baseline samples
	 Seroconversion from IgG/IgM negative-to-positive during the treatment period
	a. This is determined by ELISA from serum or plasma using baseline samples and end-of-study samples
	 Evaluation of HLA-types and germline factors associated with outcomes.
	a. This is determined by Illumina MEGA ^{EX} 6 million SNP array or targeted next generation sequencing of HLA alleles, or other germline DNA testing.
Blood	Baseline (within 3 days of starting hydroxychloroquine)
Collection Schedule	Study termination or at positive test for SARS-CoV2
Number of Participants	300
Duration of Study	Up to ~ 100 days

Background:

Due to the nature of COVID-19 infection, which is often asymptomatic in many individuals, it is conceivable that some population of enrollees in the parent trial "Pre-exposure Prophylaxis for SARS-Coronavirus-2: A Pragmatic Randomized Clinical Trial", may have already been exposed and recovered. Due to the pragmatic and emergent

PREP COVID-19

nature of the trial, participants for primary prophylaxis, the absolute nature of prior exposure cannot be determined in real time, or across all participants in the trial.

The purpose of this sub study is to allow for optional enrollment for collection of peripheral blood in health care workers at academic institutions with capabilities to collect and process peripheral blood. The peripheral blood will be used to accomplish several objectives. First, it will allow for post-hoc analyses that can determine which participants enrolled in the sub arm have had prior exposure through assessment of IgG and IgM antibodies specific to COVID-19 viral proteins. Emerging literature suggests that exposed and recovered patients or individuals develop persistent antibodies that can be detected in serum or plasma. Thus, participants with prior exposure (i.e. had presence of antibodies at baseline) can be excluded in secondary efficacy analyses. Secondly, end-of-study collection will allow for definitive assessment of the percentage of healthcare workers who seroconvert (i.e. negative at baseline, and positive at end-of-study) during the trial period in both dosing arms and the comparable placebo arms. Finally, preservation of buffy coat (white blood cells) will serve as a source of DNA and RNA that can be used for subsequent host-derived factors that contribute to drug efficacy or exposure/seroconversion rates.

OBJECTIVES

In participants from the PREP COVID-19 parent protocol, who choose to participate in this sub study, we will evaluate:

Objective 1: Circulating antibody (IgG or IgM) presence specific for COVID-19 virus protein at baseline

Endpoint 1: ELISA from serum or plasma using baseline samples

Objective 2: Seroconversion from IgG/IgM negative-to-positive during the treatment period *Endpoint 2:* ELISA from serum or plasma using baseline samples and end-of-study samples

Objective 3: Evaluation of HLA-types and germline factors associated with outcomes *Endpoint 3:* Ilumina MEGA^{EX} 6 million SNP array or targeted next generation sequencing of HLA alleles, or other germline DNA testing

STUDY CALENDAR

Parameter	Pre-Treatment	End of Treatment
Demographics	X	
Blood collection		x

Note: The sample collection schedules outlined above are based on an ideal subject. The sample schedule should be followed as closely as is realistically possible; however, the schedule may be modified (± 4 business days) due to problems such as scheduling delays or conflicts (e.g., clinic closure, poor weather conditions, vacations, etc.).

1. Within 4 days prior to starting study drug, unless otherwise noted.

2. At the end of 90 days of study drug as per parent protocol or at positive test for SARS-CoV2

3. One 10 mL EDTA tube (lavender top)

STORAGE AND SUPPLY

EDTA tubes (lavender top): Institutional own supplies will be utilized, kits will not be shipped to participating sites

Collected/ Processed/ Aliquoted Sample Storage

For ALL peripheral blood specimens collected, processed, and aliquoted:

Samples should be stored at -80C and shipped or transferred below on dry ice. Samples should be removed from -80C storage and placed directly in a dry ice-containing shipper with suitable volume of dry ice for overnight transport, taking special care in summer/warm months.

If shipment is not required (e.g. collected and processed at VUMC), samples can be batch couriered or transferred weekly to the [name] lab.

Blood Samples

PREP COVID-19

Tubes should be packed according to the Lab manual and sent immediately (within 24 h).

Peripheral blood will be collected in participants prior to initiating hydroxychloroquine under the parent protocol guidelines, and at the end of treatment (90 days or at positive test for SARS-CoV2. The molecular correlates for each biological sample/time point are listed below.

Tube	Amount	Baseline (within 3 days of enrollment)	End of study (end of 90 days or at positive test for SARS-CoV2)
EDTA tube (lavender top)	10mL (1x10mL)	Х	Х

Sample Source	Test	Needs immediate specialized processing	Needs immediate shipping
Buffycoat	RNA and DNA extraction	YES	NO
Plasma	ELISA for COVID-19 IgG and IgM		

STATISTICAL CONSIDERATIONS

Correlative analyses will be compared to clinical endpoints on the parent protocol, particularly the primary endpoint of seroconversion during the treatment period. These exploratory analyses will be performed using the baseline and end of treatment blood collections, and are primarily descriptive in nature.

Correlative analyses endpoints will be categorized as dichotomous variables. In exploratory analyses, patients will be stratified by clinical response (i.e. lack of seroconversion) to determine if the change in endpoint is associated with patient-specific clinical benefit from treatment.

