3.2 Study Outcome Measures

3.2.1 Primary Outcome Measure

[figure not shown]
• COVID-19-free survival

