3.2.2 Secondary Outcome Measures

- Incidence of confirmed SARS-CoV-2 detection
- Incidence of symptoms compatible with COVID19 (possible disease)
- Incidence of all-cause study medicine discontinuation or withdrawal
- Ordinal Scale of COVID-19 Disease Severity (for those who develop COVID-19)
 - No illness
 - Illness with outpatient observation
 - Hospitalization (or post-hospital discharge)
 - Hospitalization with ICU stay or death
- Incidence of hospitalization or death
- Self-reported adherence
- Self-reported study medication side effects

Primary outcome of COVID-19-free survival will be confirmed by positive test. Assessment of other outcome measures will be primarily by self-report. As necessary, COVID-19 disease will be verified from public health records, medical records, or death certificates.

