7.2 Laboratory Evaluations

There are no laboratory evaluations in the protocol. There is an opportunity for participants to participate in an optional lab-based sub-study. Details in Appendix A.

Clinical outcomes are by self-report.

SARS-COV2 positivity is by self-report.

Informed consent will request permission to contact local public health authorities or their medical provider in the event of loss to follow up or COVID-19 disease. Public health authorities or medical providers may verify confirmatory laboratory results.

There is no incentive to be dishonest, and we believe healthcare workers in particular will take their responsibilities seriously.

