10.4 Final Analysis Plan

We will assessCOVID-19-free survival in high-risk healthcare workers who receive hydroxychloroquine compared to those who receive placebo.

We will compare survival in a time-to-event analysis for COVID-19-free survival using Log-rank test with survival displayed as a Kaplan-Meier curve. Analysis will be intention-to-treat. Persons who develop confirmed COVID-19 or die will be considered failures. Persons lost to follow up will be censored.

Secondary endpoints for incidence will be assessed via Fisher's Exact test for the proportions by study arm. The secondary endpoint on the ordinal scale will be assessed with a proportional odds model.

PREP COVID-19

Version 1.0 27 March 2020

Among those with symptoms, severity of symptoms (recorded on a 0-10 visual analog scale) will be compared via Mann-Whitney U by study arm.

A priori subgroup analyses will include assessment by:

- Days from Exposure
- Decile of age
- Sex as a biological variable
- Censored subjects, who became symptomatic before receipt of the first dose of study medicine, will be separately analyzed and reported.

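### Appendix A misnames seroconversion as the parent trial's primary endpoint, and its benefit analysis groups people by staying negative without an arm contrast, so it can find prognostic factors but not who benefited

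*Combined protocol and SAP*

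**What the plan says.** **Parent protocol.** Section 3.2.1 gives one primary outcome, "COVID-19-free survival". Section 3.2.2 adds: "Primary outcome of COVID-19-free survival will be confirmed by positive test". Section 10.4 defines the event: "Persons who develop confirmed COVID-19 or die will be considered failures". Seroconversion is not among the secondary outcomes in section 3.2.2. Section 7.2 states: "There are no laboratory evaluations in the protocol"; blood is drawn only in the optional sub-study.

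**Appendix A, objectives.** Objective 2 of the 300-person sub-study is "Seroconversion from IgG/IgM negative-to-positive during the treatment period". Objective 3 relates HLA types and germline factors to outcomes. The paragraph on the sub-study's purpose plans the percentage who seroconvert, among those negative at baseline, in the dosing and placebo arms. It also hopes to find host factors bearing on drug efficacy or on exposure and seroconversion.

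**Appendix A, Statistical Considerations.** The endpoint sentence sets the correlates against the parent protocol's clinical endpoints, "particularly the primary endpoint of seroconversion during the treatment period". The analyses are described as exploratory and mainly descriptive. Participants are then to be grouped by clinical response, defined as not seroconverting, "to determine if the change in endpoint is associated with patient-specific clinical benefit from treatment". This section mentions no arm, placebo comparison or interaction.

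**The concern.** There are two separate problems in one short section.

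First, the endpoint is misattributed. An analyst following the text would take seroconversion as the parent's primary endpoint. For Objective 2, that means comparing seroconversion with itself.

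Second, the grouping does not match the question. In a prevention trial, staying negative is the usual outcome in every arm. A factor that is more common among people who stay negative may only mark lower exposure or lower susceptibility. To say that it marks benefit from the drug, one must show that the drug-placebo difference varies with the factor. At stake is how the sub-study's host-factor results are read: a prognostic association could be described as a predictor of drug benefit.

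**Working it through.** **1. Endpoint check, by text.**

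- Parent event: confirmed COVID-19 or death, analysed as time to event (section 10.4), with positivity self-reported (section 7.2).
- Sub-study event: a change from antibody-negative to antibody-positive by ELISA between two blood samples (Appendix A).

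The two are not interchangeable. Appendix A's background says that infection is often without symptoms, so an untested infection could seroconvert without being a parent event. Conversely, the second sample may be taken at the time of a positive test. A confirmed case who is still antibody-negative at that draw would be a parent failure but a sub-study responder. The documents do not say how often either would happen.

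**2. What the response grouping measures.**

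Suppose the drug did nothing (hazard ratio 1). Any factor that lowers infection risk would still be more common among people who stay negative, so it would be associated with response although nobody benefited. The grouping alone therefore cannot identify benefit, whatever the event rate.

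**3. Size, as an illustration.** The plan gives no figure of its own to reproduce here.

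Inputs:
- placebo risk p = 10% and hazard ratio 0.65 (section 10.2);
- seroconversion assumed to occur at the parent's event rate, because the documents give no seroconversion rate;
- the drug assumed to cause no infections;
- range for p: 8% to 20% from the section 10.2 table, and 35% from the community attack rate in section 2.2.

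Formulas:
- drug-arm risk: pt = 1 − (1 − p)^0.65
- share of drug-arm negatives who would also be negative on placebo: (1 − p)/(1 − pt)
- share whose infection was prevented: (p − pt)/(1 − pt)

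At p = 10%: pt = 1 − 0.9^0.65 = 6.6%, so 93.4% of drug-arm participants stay negative. Then 90/93.4 = 96.4%, and the prevented share is 3.6%.

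| Placebo risk | Drug-arm risk | Drug arm negative | Would be negative on placebo | Prevented by drug |
|---|---|---|---|---|
| 8% | 5.3% | 94.7% | 97.1% | 2.9% |
| 10% | 6.6% | 93.4% | 96.4% | 3.6% |
| 15% | 10.0% | 90.0% | 94.5% | 5.5% |
| 20% | 13.5% | 86.5% | 92.5% | 7.5% |
| 35% | 24.4% | 75.6% | 86.0% | 14.0% |

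With 100 per arm at p = 10%, about 187 of 200 treated participants are responders, and about 7 of them owe it to the drug. Of all responders, 90/(90 + 2 × 93.4) = 33% are on placebo.

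**4. What 300 participants can show once arm is included.**

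Assume 100 per arm, all antibody-negative at baseline and all with both samples. Expected events are 10 + 2 × 6.6 = about 23. This is a maximum at that risk, because baseline positives and missing second samples reduce it.

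Power for the simple comparison of seroconversion is Φ[(|p − pt| − z·SE0)/SE1], with SE0 pooled and SE1 unpooled. The rows below are for the two placebo risks shown:

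| Placebo risk | 100 v 100, two-sided 0.025 | 100 v 100, two-sided 0.05 | 200 v 100, two-sided 0.05 |
|---|---|---|---|
| 10% | 8% | 14% | 19% |
| 20% | 16% | 23% | 32% |

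A factor-by-arm interaction splits the same few events further and would generally be less precise still.

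**The case against.** **The appendix does compare arms.** A reader might infer that the sub-study never does so. The documents do not support that: the purpose paragraph plans seroconversion percentages by dosing and placebo arm among baseline-negatives. What stands is narrower. Those percentages give an average difference between arms, and the benefit analysis in the Statistical Considerations does not draw on them.

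**Germline factors may still be related to the parent endpoint.** A reader might infer that HLA and germline factors would never be tied to COVID-19-free survival. That is also unsupported. The text refers to parent clinical endpoints in the plural, the wording singles one out without excluding others, and Objective 3 speaks of outcomes generally. The circularity concerns Objective 2 only.

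**Silence on arm is not a decision to ignore it.** This is fair. The section is brief and specifies no model, and the purpose paragraph distinguishes factors for drug efficacy from factors for exposure. One cannot say that a prognostic factor would be reported as drug benefit, only that the stated grouping gives no protection against it.

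**The work is exploratory and small.** True, and this sets the priority. But an exploratory label limits how firmly a result is claimed; it does not turn a grouping by outcome into a measure of treatment benefit.

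**The numbers rest on an assumed rate.** Also true. If many infections are without symptoms, seroconversion could exceed 10%. The range covers this, and the qualitative conclusion holds throughout.

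**Conclusion.** The point holds in a limited form. The Statistical Considerations of Appendix A attribute to the parent protocol a primary endpoint that it does not have, and they relate non-seroconversion to treatment benefit without stating an arm contrast. As written, that grouping can identify prognostic factors but not who benefited.

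If seroconversion follows the parent's 10% placebo risk and hazard ratio of 0.65, and the drug causes no infections, about 96% of drug-arm negatives would have been negative anyway. The figure is about 86% to 97% for placebo risks of 35% to 8%. These percentages are illustrative; the logical point does not depend on them.

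A reader might go further and infer that the parent trial's endpoint or conclusion is in doubt. It is not: sections 3.2.1, 3.2.2 and 10.4 agree on COVID-19-free survival, and the fault lies in an exploratory sub-study of 300. This is a minor-priority correction.

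**What to change.** In the Statistical Considerations of Appendix A:

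1. Name COVID-19-free survival as the parent primary endpoint and seroconversion as a sub-study endpoint.
2. Bring in the by-arm comparison of seroconversion among baseline-negatives that the purpose paragraph already plans.
3. Replace the grouping by non-seroconversion with an exploratory factor-by-arm estimate (drug v placebo), with a confidence interval and on a stated scale. Drop the term clinical response for people who simply stay negative.
4. Describe any association without an arm contrast as prognostic, not as treatment benefit.

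The cost is rewording one short section and fitting a different model to the same data; no extra samples or visits are needed. The drawback is precision. With at most about 23 expected events under the 10% assumption, interaction estimates will be very wide and should be presented as descriptive only.

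### Appendix A sub-study: a confirmed case who is still antibody-negative at the positive-test blood draw is classed as a clinical response

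*Combined protocol and SAP*

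**What the plan says.** Appendix A plans two blood samples per participant. The summary table sets the second at "Study termination or at positive test for SARS-CoV2", and the calendar footnote puts it "At the end of 90 days of study drug as per parent protocol or at positive test for SARS-CoV2". The blood-sample text and the tube table repeat the alternative of a draw at the positive test. No later sample is planned for someone who has tested positive. The one flexibility is that "the schedule may be modified (± 4 business days") for scheduling problems.

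The background section counts people who "seroconvert (i.e. negative at baseline, and positive at end-of-study) during the trial period". It explains the value of serology by saying that "exposed and recovered patients or individuals develop persistent antibodies that can be detected in serum or plasma".

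The appendix's statistical section says that "patients will be stratified by clinical response (i.e. lack of seroconversion"), and gives the purpose as "to determine if the change in endpoint is associated with patient-specific clinical benefit from treatment". It refers to clinical endpoints of the parent protocol, "particularly the primary endpoint of seroconversion during the treatment period". It also calls these analyses exploratory and mainly descriptive.

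In the parent protocol, the primary outcome is COVID-19-free survival (section 3.2.1), confirmed by a positive test (section 3.2.2). Section 10.4 treats confirmed COVID-19 as a failure. Seroconversion is not among the secondary outcomes in section 3.2.2.

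**The concern.** The response label depends on serology alone, and for a confirmed case that serology is fixed at the moment of diagnosis. The appendix's own rationale concerns antibody in people who have been exposed and have recovered. A sample taken at the positive test need not come from someone who has recovered. If antibody is absent at that draw, the person reads as negative-to-negative, which the plan equates with response and then relates to benefit from treatment.

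The sampling rule also treats infected people differently according to whether they were tested. An infected participant who is never tested is sampled at the end of the study, when antibody may have had longer to appear. One who tests positive is sampled at once. The best-documented infections are therefore the most exposed to the wrong label.

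At stake are the by-arm seroconversion rates (Objective 2) and any stratification of HLA or germline results by response (part of Objective 3). The sentence naming seroconversion as a parent primary endpoint adds to the confusion, because the two definitions classify the same person in opposite ways.

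**Working it through.** The plan gives no figure to reproduce: the 300 in the appendix has no power calculation. The check applies the stated definitions to one participant and then sizes the result.

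**Definitions applied to a baseline-negative participant who tests positive**

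1. The final sample is taken at the positive test (Appendix A, blood collection schedule and tube table).
2. If that sample is antibody-negative, the participant has not seroconverted (Appendix A, background).
3. Lack of seroconversion is clinical response (Appendix A, statistical considerations).
4. No rule in the appendix makes a positive test a non-response.
5. The parent analysis counts this participant as a failure (section 10.4).

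Steps 3 and 5 conflict. This follows from the text and needs no outside fact.

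**Size**

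Inputs from the documents: 300 participants (Appendix A); placebo COVID-19-free survival of 90% and hazard ratio 0.65 (section 10.2).

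Assumptions: 100 per arm; the same risks as in the parent trial; no losses; all participants seronegative at baseline; no seroconversion outside the confirmed cases; f, the share of confirmed cases antibody-negative at the draw, equal across arms. The documents do not give f, so it runs from 0 to 100%.

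- Risk per active arm: 1 − 0.90^0.65 = 0.0662
- Expected confirmed cases: 100 × 0.10 + 200 × 0.0662 = 10.0 + 13.2 = 23.2
- Mislabelled cases: 23.2 × f
- Labelled responders: 300 − 23.2 + 23.2 × f
- Placebo-minus-active difference in seroconversion contributed by confirmed cases: (10.0 − 6.6) × (1 − f) percentage points

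| f | Mislabelled | Labelled responders | Share mislabelled | Confirmed cases left as seroconverters | Difference (points) |
|---|---|---|---|---|---|
| 0% | 0 | 276.8 | 0% | 23.2 | 3.4 |
| 25% | 5.8 | 282.6 | 2.1% | 17.4 | 2.5 |
| 50% | 11.6 | 288.4 | 4.0% | 11.6 | 1.7 |
| 75% | 17.4 | 294.2 | 5.9% | 5.8 | 0.8 |
| 100% | 23.2 | 300.0 | 7.7% | 0 | 0 |

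With no drug effect (hazard ratio 1) there are 30 expected cases, of which 0 to 30 are mislabelled, at most 30/300 = 10% of labelled responders. Undiagnosed seroconverters or exclusion of baseline-positive participants would shrink the responder group and raise these shares somewhat.

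**After the change of definition**

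If a positive test counts as non-response whatever the serology, the number mislabelled is 0 at every f, and all 23.2 (or 30) cases sit in the non-response group.

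**The case against.** The strongest reply is that the size is unknown and may be small. The documents do not say that active cases lack antibody; they say only that recovered people have it. The assay covers IgM as well as IgG. The appendix describes infection as often without symptoms, so a positive test need not mark early infection. The trial runs no SARS-CoV-2 tests itself: positivity is self-reported (section 7.2) and asked about weekly (section 4.3.4), so with the scheduling window the draw may follow the test by some days. All of this stands against putting any floor under f. A reader might infer that at least half of the confirmed cases would be mislabelled, but nothing in the documents supports that. None of it removes the rule, and the scheduling window is not a planned convalescent sample.

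A reader might also infer that the plan counts failures as responders to the drug. The label is not arm-specific: antibody-negative placebo participants and people never exposed meet it too.

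On reach, the sub-study is optional and descriptive, and no parent endpoint, boundary or decision uses it. Objective 3 concerns outcomes generally, and the appendix also plans comparison with parent clinical endpoints, where confirmed cases remain failures. The genetic work is therefore affected only where it uses the serological response label. These limits stand and bear on the weight of the point.

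Finally, the draw at the positive test has a use of its own: its buffy coat supplies RNA from the time of infection, which a later sample cannot replace. That stands against requiring the draw to be moved.

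**Conclusion.** The response definition is wrong as written. It can place a confirmed case in the response group while the parent trial counts that person as a failure, and the sentence on the parent primary endpoint is incorrect. The misclassification follows from the text; its frequency does not. On the stated assumptions, 0 to about 23 of about 23 confirmed cases could be mislabelled, and about 12 if half are antibody-negative at the draw. The responder group is only modestly diluted, but the small seroconverter group could lose anything from none to all of its confirmed cases, and the by-arm contrast that those cases contribute would shrink in proportion.

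A reader might infer a threat to the trial's main result. The documents do not support that: the parent primary analysis does not use sub-study serology. The point is worth correcting because the analyses are meant to speak to treatment benefit and the correction is simple.

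**What to change.** In Appendix A:

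- Define sub-study infection as a positive SARS-CoV-2 test or seroconversion, and response as neither. Restrict this to participants seronegative at baseline, since someone already positive cannot seroconvert.
- Use this definition for the by-arm comparison and for the HLA and germline stratification.
- Correct the sentence on the parent primary endpoint to COVID-19-free survival, and describe seroconversion as a sub-study endpoint.
- If the draw for confirmed cases stays at the positive test, do not call the serology-only seroconversion rate by arm definitive, as the background section now does.

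These are wording changes. They use test results already asked for at the weekly visits and add no blood draws.

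Changing the draw time for confirmed cases is optional and is not needed to correct the label. Moving the draw to study termination would make the serology more informative and keep two draws per person, but would give up the infection-time RNA sample. Adding a later sample would keep both, at the cost of one extra draw for each confirmed case, about 23 on the illustration above.
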